# Cognitive behavioral therapy for cocaine addiction to improve antiretroviral medication adherence in HIVpositive patients

# [name]

# A. Study Purpose and Rational

Many research studies have revealed that highly active antiretroviral therapy (HAART) improves HIV-related clinical outcomes, such as decreased opportunistic infections and prolonged survival as well as improves surrogate markers such as HIV viral load and CD4 cell counts [1,2]. Furthermore, optimal adherence to HAART regimens is necessary to obtain adequate viral suppression [3-5] and to avoid the emergence of viral resistance [6]. Patients who are actively abusing illicit drugs, including cocaine, have been shown to demonstrate decreased adherence to HAART as well as inferior virologic and immunologic responses to therapy as compared to both former and non-drug users [7]. Therefore, it is likely that helping these patients eliminate their illicit drug use may improve their adherence to HAART and their HIV clinical outcomes. The purpose of this study is to show that providing active cocaine abusers with cognitive behavioral therapy aimed at relapse prevention and coping skills training will increase their HAART regimen medication adherence as assessed by a self-adherence questionnaire over a 4 month period.

# B. Study Design and Statistical Analysis

This is a randomized-controlled prospective study designed to assess whether or not a behavioral treatment for cocaine abuse will improve adherence to HAART therapy. The primary outcome of this study is a comparison of adherence to the prescribed HAART regimen in the intervention arm versus the standard of care arm as measured by a standardized three day recall self-assessment questionnaire administered every two weeks throughout the study. The secondary outcomes include viral suppression to undetectable levels using the RT-PCR assay (Roche) of HIV-1 viral load after 4 months and magnitude of change in the log10 viral load from baseline to the 8-week visit. The endpoint of 4 months was chosen, as most individuals who achieve undetectable viral loads will have done so by this time point [1].

Once subjects are identified as cocaine users and express interest in treatment for cocaine abuse, they will be recruited, assessed to see if they fulfill all of the inclusion/exclusion criteria, consented and randomized to either the treatment/intervention arm or the standard of care arm. Randomization will be achieved by selecting an unlabeled sealed envelope from a box containing as many envelopes as potential subjects. Half of the envelopes will say "treatment arm" and half will say "standard of care". In this way, subjects will be randomized.

Subjects in the standard of care arm of the study will be provided with a list of referrals for substance-abuse treatment including Narcotics Anonymous, individual psychotherapy and rehabilitation programs at the first visit. They will be asked to return once each week for the first 6 weeks of the protocol and then every 2 weeks for the remainder of the study period, which is a total of 4 months. At each of these visits, they will be asked to provide a urine sample that will be tested for cocaine. They will also complete the 3-day adherence questionnaire with one of the investigators every two weeks. These subjects will be provided with additional drug treatment information by the regular clinic social workers and medical practitioners only if they request it according to the current standard of care. At the end of the study, they will be asked which if any of the cocaine treatment resources they utilized. Also, on the last visit, they will complete the Marlowe-Crowne social desirability questionnaire to assess the truthfulness of their self-reported data as compared to the treatment group.

Subjects in the treatment group will have the same number of visits with the same frequency as the standard of care arm, but in addition to providing urine samples every week and completing the adherence questionnaires every two weeks, they will be asked to attend to a 45 minute session at every visit with a trained addiction professional for a session of cognitive behavioral therapy specifically designed to address relapse prevention and coping skills training. Like the standard of care arm, they will be assessed with the Marlowe-Crowne at the last visit and asked about any other addiction treatments they utilized during the study period.

182 subjects will be enrolled in this study, with half participating in each of the two arms. This number will provide enough power to analyze the primary and secondary study outcomes as described below.

The primary outcome variable is percentage of total prescribed medication doses taken as assessed by a 3 day self-report adherence questionnaire. The percentage of total prescribed doses taken will be compared in the two arms with a  $X^2$  test. Prior studies of non-drug abusers have shown that most patients report approximately a 70-80% adherence rate over the week prior to questioning with a standard deviation of around 20[8]. This self-reported adherence rate correlates with an actual adherence rate of around 55% as measured by microelectronic monitoring systems [8]. In other words, patients usually over report adherence by approximately 15-20% in a reproducible manner that still predicts changes in viral load. There is little data looking at self-reported adherence in a drug abusing population. One study has shown however that 32% of drug users obtain a viral load <400 copies/ml compared to 45% of non-users. The approximately 45% virologic response in non-users in this study is similar to the electronically monitored compliance of 55% in the previous study [7]. The lessened virologic response may be a result of pharmocokinetics and pharmocodynamics as well as viral resistance. Therefore, based on prior studies, non-users of drugs are likely to self-report around 70% adherence. Given, the lack of significant data on active drug abusers, 50% self-reported adherence is a reasonable estimate. To detect this difference, 17 subjects in each group are required.

To detect a  $0.9 \log_{10}$  difference in change in HIV-1 RNA viral load at 8 weeks (the time interval it takes to detect a  $1 \log_{10}$  change in viral load according to national guidelines) between groups assuming a standard deviation of 1.5 by unpaired t-test, a sample size of 45 subjects in each arm is required. Change in viral load is defined as the difference in  $\log_{10}$  copies/ml between the value measured at the time of the initial visit and the value at the 8-week visit. In a study comparing drug users and non-users, a  $0.9 \log_{10}$  difference was detected ( $0.8 \log_{10}$  change in the drug users and a  $1.7 \log_{10}$  change in the non-users) [7].

To compare the proportion of subjects who obtain undetectable HIV-1 RNA viral loads at 16 weeks in the two arms a  $X^2$  test will be performed. In order to have power to detect a 20% difference between groups, assuming 40% will achieve undetectable levels in treatment arm and 20% will achieve undetectable levels in the standard of care arm, 91 subjects are required in each group.

Multiple linear regression analysis of the data will be performed to correlate adherence with other variables including age, gender, ethnicity, percentage of urine samples positive for cocaine during the study, utilization of alternate treatment modalities, and other variables shown to affect adherence in other research such as drug side effects or not being able to meet food and water requirements of the regimen [8b].

Data will be analyzed by an intention to treat analysis.

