#### C. Study Procedure

All subjects participating in the study are to be followed by medical care providers in the outpatient HIV clinic and all medical management will be left to the discretion of those providers. The time intervals chosen in this study for checking viral loads after the initiation of HAART therapy correspond with national treatment guidelines [9]; however additional blood tests are at the discretion of the medical provider. Although it is not possible to blind this study, no data will be shared with either the subjects or their providers. The study period will last 4 months. Study visits will occur once a week for the first 6 weeks and then every 2 weeks thereafter. Subjects in both arms will have a urine dip test to

Columbia University College of Physicians and Surgeons

check for cocaine at every visit which will only take 5 minutes to collect and process. Also, every two weeks the subjects will be asked the questions on the 3-day adherence questionnaire to assess their medication adherence. The questionnaire will take about 15 minutes at these visits. The urine samples and questionnaires will be completed with an investigator in the HIV outpatient clinic prior to any medical visit that subject might have that day. The subjects in the treatment arm will have therapy sessions in the addiction medicine research clinic on the same days as their other study activities. All subjects will receive compensation for coming to the scheduled visits and providing urine samples in the form of vouchers. They will receive a \$15 voucher at each visit in the form of subway fare (Metrocard) or a voucher to a local fast food chain. If they complete the study and come to all of the scheduled visits, they will receive a \$50 gift certificate to Old Navy.

At the first visit, informed consent will be obtained and the study will be explained to the patient by one of the investigators. Also, the primary medical provider will initiate HAART therapy. Because adherence to the prescribed regimen is the primary outcome, patients may be placed on any of the "strongly recommended" regimens according to current national guidelines [9] at the discretion of the primary medical provider as long is the regimen is a class sparing regimen. (e.g. NNRTI-sparing, PIsparing or a PI- and NNRTI-sparing regimen) The medical care provider will choose a regimen at the first study visit while still blinded to which arm of the study the patient is in to avoid biasing the choice.

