# I. Confidentiality of Study Data

None of the data being collected during the study will be shared with the medical providers, the subjects or anyone else other than the primary investigators. Each subject will be assigned a unique identifier code number to identify his or her data (lab tests, drug tests, questionnaire data). This number will have no relationship to the arm of the study the subject is participating in. Hence, the support staff performing urine drug tests, serologic tests (viral loads and CD4 counts) and administering the adherence questionnaires will be blinded to which arm of the study the patient is participating in. All data will be stored in a secure database accessible only to the investigative team.

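### Allocation by unnumbered envelopes drawn from a box, with no order or log described, leaves a redrawn or discarded envelope hard to detect in a trial that cannot be blinded

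*Protocol*

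**What the plan says.** Protocol section B sets out the allocation procedure: "Randomization will be achieved by selecting an unlabeled sealed envelope from a box containing as many envelopes as potential subjects". Half of the envelopes name one arm and half the other. Subjects are first checked for eligibility and are then "consented and randomized to either the treatment/intervention arm or the standard of care arm". The same section fixes the size and ratio: "182 subjects will be enrolled in this study, with half participating in each of the two arms".

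Three statements elsewhere bear on how well this is protected:

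- Section C, on blinding: "Although it is not possible to blind this study, no data will be shared with either the subjects or their providers".
- Section C, on the choice of antiretrovirals, says of the treating clinician: "will choose a regimen at the first study visit while still blinded to which arm of the study the patient is in".
- Section I, on the subject code: "This number will have no relationship to the arm of the study the subject is participating in".

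No section says who prepares the envelopes, who draws, whether the draw is recorded, or what is done with an envelope once opened.

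**The concern.** In a box of unmarked envelopes, any envelope is a legitimate next one. There is no sequence to compare the allocations with, and no described record of which envelope belonged to which subject. If an envelope were opened, set aside and replaced by another, the trial's papers as described would look the same.

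The setting gives a reason to care. Entry requires an interest in stopping cocaine use. One arm offers a 45-minute therapy session at every visit and the other a list of referrals, so subjects and recruiters may both hope for the therapy arm. The primary outcome is self-reported adherence, which motivation can plausibly affect. If the more motivated subjects were steered into CBT, part of the observed difference would reflect who they were and not the therapy. Analysis by intention to treat (section B) would not remove this, because it takes the recorded allocation as given.

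A smaller question is whether a box sized to potential subjects delivers the equal arms that section B promises.

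**Working it through.** **1. The planned arm size.** Section B bases 91 per arm on undetectable viral load at 16 weeks, "assuming 40% will achieve undetectable levels in treatment arm and 20% will achieve undetectable levels in the standard of care arm". Alpha and power are not stated; I assume two-sided 5% and 80%.

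- Without continuity correction: n = [1.96 × √(2 × 0.3 × 0.7) + 0.842 × √(0.4 × 0.6 + 0.2 × 0.8)]² / 0.2² = 81.2, so 82 per arm.
- With continuity correction: (81.2 / 4) × [1 + √(1 + 4 / (81.2 × 0.2))]² = 90.9, so 91 per arm. The plan's figure is reproduced.

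**2. Does the draw give 91 and 91?** The number of potential subjects is not given, so the box size M is an assumption. With 182 draws without replacement from M envelopes, half per arm, the size of one arm is hypergeometric with SD = √(182 × 0.25 × (M − 182) / (M − 1)).

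| M | SD | 95% range of one arm | Chance of exactly 91/91 |
|---|---|---|---|
| 182 | 0 | 91 | 100% |
| 200 | 2.0 | 87 to 95 | 19% |
| 300 | 4.2 | 83 to 99 | 9% |
| 400 | 5.0 | 81 to 101 | 8% |

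If the box holds 182 but only 150 subjects enrol, one arm ranges from 70 to 80 instead of 75.

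Power for 40% against 20%, without continuity correction, is 84.3% at 91/91. At 81/101 it is 83.7% to 84.2%, depending on which arm is smaller. The loss is under 1 point.

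**3. Can a draw be traced?** I looked in the protocol for each thing that would let a monitor confirm an allocation.

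- Number or order on the envelope: none; section B calls the envelopes unlabeled.
- Link from envelope to subject: none described. The code in section I is unrelated to arm, as it should be, and nothing else makes the link.
- Log of draws, or a rule against a second draw: none described.
- Separation of preparer and recruiter: not described.
- Steps before the draw: eligibility and consent come first (section B).
- Regimen choice: made blind to arm (section C).

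The last two protect the decision to enrol and the choice of regimen. They do not show whether the envelope opened was the only one drawn.

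**4. Size of a possible bias, for illustration.** Two inputs are assumptions that the protocol does not supply: 9 of 182 subjects (about 5%) are steered, and each adheres 20 points better than average.

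- If nine such subjects replace average subjects in CBT and standard care is unchanged: 9 / 91 × 20 = 2.0 points.
- If nine such subjects drawn to standard care are exchanged with nine average CBT subjects, both means move: 2 × 9 / 91 × 20 = 4.0 points.

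For scale, section B quotes an SD of around 20 for non-users. With 91 per arm the standard error of a difference in means is 20 × √(2 / 91) = 2.96 points. The difference detectable with 80% power is about 2.80 × 2.96 = 8.3 points. Section B plans for 20 points (70% against 50%). With no true effect, a bias of 2 points would raise the chance of a significant result favouring CBT from 2.5% to about 10%; a bias of 4 points would raise it to about 27%. These rates treat adherence as a mean with that SD, so they too are only a guide.

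**The case against.** The best defence is that a draw from a mixed box is proper randomization if the procedure is followed, and nothing in the protocol permits a second draw. The envelopes are sealed, and being unlabeled also means that the outside does not reveal the arm. Custody and logging are often left to a procedures manual. This much stands: the weakness concerns proof and deterrence, and the chance mechanism itself is sound. It does not dispose of the point, because section B fixes the mechanism, and an unmarked envelope has no order against which any manual could check it.

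Four stronger readings are tempting, and the documents do not support them.

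- A reader might infer that a redraw could never be found. That goes too far. A returned envelope would have a broken seal, a discarded one would leave the count short if the box had been counted, and baseline viral load, CD4 count and drug screening score could be compared by arm. These checks are imperfect, since the protocol describes no count and no scale of motivation, so hard to detect is the right wording.
- A reader might infer that section B contradicts its own equal split. Read together, its statements may simply mean 182 envelopes, which gives exactly 91/91. The text is loose because it never says so.
- A reader might infer that unequal arms open the way to selection bias. They do not; unequal numbers by themselves bias nothing.
- A reader might infer that the arm mix will drift over the two years of recruitment. Drawing without replacement from a half-and-half box has no systematic trend.

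**Conclusion.** The point holds as one of concealment and traceability. The protocol prescribes envelopes without number or order and describes no record tying an envelope to a subject, in a trial that cannot be blinded and whose primary outcome is self-reported. Departures from the draw would be hard to detect.

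That the bias would run toward CBT assumes that anyone steering would favour the therapy arm and that the subjects steered adhere better. The 2 to 4 points rest on the assumed nine subjects and 20-point advantage. The documents give no ground for saying that steering will occur, and a reader should not conclude that the result will be biased.

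The split is a secondary matter of wording, with negligible effect on power. The change is worth making before enrolment because it is cheap and the missing trail cannot be recreated afterwards.

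**What to change.** Replace the box draw in section B with the following:

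- Existing staff who do not recruit prepare a computer-generated list of 182 allocations, 91 per arm. Blocks of varying size are optional; they keep the arms close in number if recruitment stops short, but the end of a block can be guessed in an unblinded trial, so block sizes should not be disclosed to recruiters.
- The list goes into exactly 182 sequentially numbered, opaque, sealed envelopes.
- Each envelope is opened strictly in order, and only after consent, eligibility and the regimen choice have been recorded.
- The subject code and date are written on the envelope before it is opened.
- A log of assignments is kept apart from the staff whom section I describes as blinded, so that the code itself still says nothing about the arm.

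This also settles the split, since the number of envelopes is then stated. The cost is a few hours of preparation and the upkeep of a simple log, with no extra staff or subjects.

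### Adherence is measured about eight times per subject, but the primary comparison is one undated chi-square test with no stated summary over visits or unit of analysis

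*Protocol*

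**What the plan says.** Section A gives the aim: cognitive behavioral therapy "will increase their HAART regimen medication adherence as assessed by a self-adherence questionnaire over a 4 month period". Section B says adherence is compared between arms "as measured by a standardized three day recall self-assessment questionnaire administered every two weeks throughout the study". It then defines the variable: "The primary outcome variable is percentage of total prescribed medication doses taken as assessed by a 3 day self-report adherence questionnaire". The test follows: "The percentage of total prescribed doses taken will be compared in the two arms with a" chi-square test.

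Section C adds "The study period will last 4 months", and says of the first visit: "Also, the primary medical provider will initiate HAART therapy". There is therefore no adherence to recall at that visit, and the first informative questionnaire falls at about week 2.

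Both secondary outcomes in section B carry a date and a test: change in log10 viral load at week 8 by t-test, and undetectable viral load at week 16 by chi-square. The primary outcome carries a test but no date, no rule for combining the two-weekly questionnaires, and no statement of whether the subject or the dose is counted.

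**The concern.** The time point and the summary over visits are part of the definition of an endpoint. The protocol treats them that way for its secondary outcomes, but not for the one that decides the trial.

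Two things are at stake. First, a chi-square test needs counts. A percentage per subject is not a count, and no cut-off for an adherent subject is given. The reading that needs nothing added to the text is to count doses taken and doses prescribed in each arm over all visits. That treats repeated doses from one person as independent, which overstates the information and inflates the false-positive rate.

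Second, if the analyst instead moves to a subject-level analysis, the text does not say whether the last visit or the mean over visits decides. That choice could be made after the data are seen.

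**Working it through.** **Inputs from the protocol.** Section B: SD about 20 points for one self-report, adherence 70% against 50%, 17 per group for the primary outcome, 182 subjects in two equal arms (91 each). Sections B and C: a questionnaire every 2 weeks for 4 months, so 16/2 = 8 per subject.

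**Assumptions.** Two-sided alpha 5% and power 80%, neither of which is stated; equal correlation ρ between a subject's visits, 0.3 to 0.7; 6 to 18 doses per 3-day recall; SD 20 as the total SD of one visit's percentage.

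**1. The plan's own figure.** For two means with difference 20 and SD 20, n = 2 × (1.96 + 0.84)² × (20/20)² = 15.7, or 16; the t-based solution is 16.7, so 17 per group. This reproduces the plan. As a chi-square with one yes/no result per subject, 70% against 50% needs 93 per group. The 17 thus comes from a comparison of subject-level means, not from the named test.

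**2. SD of a subject's mean over 8 visits.** SD = 20 × √((1 + 7ρ)/8).

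| ρ | Variance | SD |
|---|---|---|
| 0.3 | 400 × 3.1/8 = 155 | 12.4 |
| 0.5 | 400 × 4.5/8 = 225 | 15.0 |
| 0.7 | 400 × 5.9/8 = 295 | 17.2 |

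**3. Chi-square on pooled doses, no true effect.** With d doses per recall and adherence p, the test assumes a per-subject variance of 10,000 × p(1 − p)/(8d). The test statistic is too variable by r = √(true variance / assumed variance), and the false-positive rate is 2 × [1 − Φ(1.96/r)].

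- Low end (p = 0.5, d = 6, ρ = 0.3): assumed variance 2,500/48 = 52.1; r = √(155/52.1) = 1.73; rate 0.26.
- Middle (p = 0.5, d = 6, ρ = 0.5): r = √(225/52.1) = 2.08; rate 0.35. Simulation with percentages truncated to 0–100 gave 0.33.
- High end (p = 0.7, d = 18, ρ = 0.7): assumed variance 2,100/144 = 14.6; r = √(295/14.6) = 4.50; rate 0.66.

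**4. Week 16 and the subject mean both left open, no true effect.** The two test statistics have correlation √((1 + 7ρ)/8) = 0.62, 0.75, 0.86. The chance that at least one exceeds 1.96 in absolute value is 0.087, 0.081, 0.074.

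**5. Assumed 6-point constant effect, 91 per arm.** For week 16, SE = 20 × √(2/91) = 2.96, 6/2.96 = 2.02, power about 52%. For the mean:

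| ρ | SE of difference | 6/SE | Power of mean | Trials where the two differ in significance |
|---|---|---|---|---|
| 0.3 | 1.85 | 3.25 | 90% | 40% |
| 0.5 | 2.22 | 2.70 | 77% | 30% |
| 0.7 | 2.55 | 2.36 | 65% | 20% |

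**6. The planned 20-point difference, held constant.** Week 16: 20/2.96 = 6.7. Mean at ρ = 0.5: 20/2.22 = 9.0. Both reject in essentially every trial, so the choice between them does not matter there.

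**The case against.** The strongest reply is that the text is less open than it looks. The wording about adherence points one way: "as assessed by a self-adherence questionnaire over a 4 month period" in section A, two-weekly administration throughout in section B, and a percentage of the total prescribed. Section B also plans to regress adherence on a whole-period covariate, the share of cocaine-positive urines. This stands: a whole-period summary is implied. It is not stated, however, and even if it is accepted, the text does not say whether doses are pooled or averaged within subjects. Step 3 shows that this matters.

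Several stronger readings are tempting but not supported:

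- A reader might infer that section B sets week 16 for adherence through "The endpoint of 4 months was chosen, as most individuals who achieve undetectable viral loads will have done so by this time point". The reason given is virologic, and nothing ties it to adherence.
- The singular reference to a 3-day questionnaire names the instrument (section F). It does not mean one administration.
- The SD of 20 is a planning value from the literature, for recall over a week. It does not define the endpoint.
- A reader might infer eight separate tests with uncontrolled error. No section plans visit-by-visit testing, and since one primary comparison is named, no ordering of tests or division of alpha is needed for it.
- A reader might infer that the readings could contradict each other in direction. The calculations show significant against non-significant, not a reversed effect.

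It can also be said that summarising repeated measures belongs in a statistical analysis plan. That would cover modelling detail. It does not cover a test already fixed in the protocol that does not suit the data, nor an undated primary outcome beside dated secondary ones.

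**Conclusion.** The point holds in a limited form: the primary comparison is under-defined, and the test named for it is unsuitable for repeated dose percentages. The largest consequence is the pooled-dose chi-square, with a false-positive rate of about 0.26 to 0.66 against an assumed nominal 0.05. That range rests on the assumed doses per recall, adherence level and correlations; the inflation would vanish only if doses behaved as independent trials, which is implausible for adherence. The choice between week 16 and the mean is a smaller matter: type I error of about 0.07 to 0.09, and differing significance in about 20 to 40% of trials for an effect of 6 points, a figure that is not in the protocol. Under the protocol's own 20-point difference, held constant, that choice changes nothing. The plan should be amended, but the documents do not show that the trial's conclusion would be wrong under every reasonable reading.

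**What to change.** In section B, define the primary outcome as each subject's mean percentage of prescribed doses taken over the scheduled two-weekly questionnaires from week 2 to week 16. Compare the arms once, with the subject as the unit, by a two-sample t-test (or a linear model) at two-sided 5%. State that this replaces the chi-square test for adherence; naming the mean alone would leave a test that cannot assess a difference in means. Label week-16 and visit-by-visit comparisons descriptive. The handling of missed questionnaires then has to be settled too, here or in the analysis plan.

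The cost is a few sentences. No visits, data or subjects are added: at a 20-point difference the eight-visit mean needs about 7, 9 or 12 per arm at ρ = 0.3, 0.5 or 0.7 (normal approximation), below the 17 stated and far below the 91 planned. The change also brings the test into line with the calculation behind the 17. The small downside is that an effect emerging late is diluted by the early visits. For example, an effect rising linearly from 0 at week 2 to 20 points at week 16 averages 10 points; at ρ = 0.5, 10/2.22 = 4.5, so the mean would still detect it in about 99% of trials, and the descriptive week-16 comparison would show its size.

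### The chi-square test named for the primary outcome does not fit a per-subject percentage of doses taken, and the stated 17 per group is a t-test figure

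*Protocol*

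**What the plan says.** All of this is in Protocol section B, Study Design and Statistical Analysis.

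- **Outcome:** "The primary outcome variable is percentage of total prescribed medication doses taken as assessed by a 3 day self-report adherence questionnaire".
- **Repetition:** adherence is "measured by a standardized three day recall self-assessment questionnaire administered every two weeks throughout the study", which over 4 months is about 8 questionnaires per subject.
- **Test:** "The percentage of total prescribed doses taken will be compared in the two arms with a" chi-square test.
- **Planning values:** an SD of around 20 for reported adherence, from earlier work in people described as not abusing drugs; "non-users of drugs are likely to self-report around 70% adherence"; and for active users, "50% self-reported adherence is a reasonable estimate".
- **Sample size:** "To detect this difference, 17 subjects in each group are required". No test, alpha or power is stated beside this figure.
- **Enrolment:** 182 subjects, 91 per arm. This number is set by the secondary outcome of undetectable viral load.

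For the other outcomes the section matches test to data type. The change in log10 viral load gets an unpaired t-test, and the proportion of subjects with undetectable virus gets a chi-square test. Adherence itself is later put into a multiple linear regression, which treats it as a continuous variable.

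**The concern.** A percentage with an SD is a continuous value for each subject. A chi-square test works on independent counts, so it can be applied to this outcome in only two ways.

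1. Class each subject as adherent or not. The protocol gives no threshold, and the percentage it defines as the outcome is then discarded. A threshold left open on a primary outcome can also be chosen after the data are seen.
2. Count doses taken and missed across each arm. The subject is the unit randomised, and one subject's doses are correlated with each other. Treating them as independent makes the standard error too small.

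The test is the one on which the trial's main claim rests. The sample size printed in the same paragraph appears to come from a different test, so a reader cannot tell from the protocol which analysis was intended.

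**Working it through.** **Inputs from the protocol:** adherence 70 v 50, SD about 20, 17 per group for the primary outcome, 91 per arm enrolled.

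**Assumptions:** two-sided 5% and 80% power. Neither is stated, but step 2 supports them.

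**Step 1. Reproduce the 17.** The standardised difference is d = (70 − 50)/20 = 1. The two-sample t-test (noncentral t) gives n = 16.7 per group, rounded up to 17, with power 80.7% at 17. The stated figure is reproduced.

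**Step 2. Check the assumed alpha and power against the other two sample sizes.**
- Viral load change: d = 0.9/1.5 = 0.6 gives 44.6, so 45, as stated.
- Undetectable virus, 40% v 20%, chi-square with continuity correction: 90.95, so 91, as stated.

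**Step 3. Try the named test.** For a chi-square of 70% v 50%, with mean proportion 0.60:

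n = [1.96·√(2·0.60·0.40) + 0.8416·√(0.70·0.30 + 0.50·0.50)]² / 0.20² = (1.358 + 0.571)² / 0.04 = 93 per group.

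With continuity correction, (n/4)·[1 + √(1 + 4/(n·0.20))]² = 102.8, so 103. The smallest variant tried (one-sided, 80% power, uncorrected) still needs 74. The 17 is not a chi-square figure.

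**Step 4. Type I error if doses were pooled.** Let m be the doses per subject and p = 0.60 the common mean (midway between 50 and 70). If SD is the spread of true adherence between subjects, the variance of the pooled comparison is understated by

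D = 1 + (m − 1)·ρ, with ρ = SD²/[p(1 − p)],

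and the actual two-sided error is 2·[1 − Φ(1.96/√D)]. If 20 is instead the SD of the observed percentages, D = m·SD²/[p(1 − p)].

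Doses per day are not in the protocol. I take 2 to 6 per day over 3 days: 6 to 18 doses for one questionnaire, and up to 6 × 3 × 8 = 144 for eight. ρ is 0.01/0.24 = 0.042 for SD 10 and 0.04/0.24 = 0.167 for SD 20.

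| Doses per subject | SD used | D | Error by formula | Error by simulation, 91 per arm |
|---|---|---|---|---|
| 6 | 20, observed | 1.00 | 5% | 4% |
| 6 | 10, true | 1.21 | 7% | 8% |
| 6 | 20, true | 1.83 | 15% | 15% |
| 18 | 10, true | 1.71 | 13% | 14% |
| 18 | 20, true | 3.83 | 32% | 33% |
| 144 | 10, true | 6.96 | 46% | 47% |
| 144 | 20, true | 24.8 | 69% | 71% |

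The simulations are beta-binomial with no true effect. In the same setting a t-test on the subject percentages stayed at about 5%. The error is two-sided, so about half of each figure is a false result in favour of CBT and the other half favours standard of care.

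**Step 5. Power at the enrolled size.** By t-test with d = 1 and 91 per arm, power exceeds 99.9%.

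**The case against.** The strongest reply is that the protocol never says doses are the unit of analysis. Its linear regression of adherence points the other way, to one value per subject. A reader might infer from the chi-square wording that the trial will pool doses and so will often declare CBT effective when it is not. The text does not support that. Pooling is one of two ways to carry out the named test, and only about half of any inflated error would favour CBT.

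The size of the inflation is also uncertain. It depends on doses per subject, on how the two-weekly questionnaires are combined, and on an SD taken from a one-week recall in people described as not abusing drugs. At 6 doses with an observed SD of 20 there is almost none.

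A reader might also infer from the 93 or 103 per group that the trial is too small. That does not follow. The 70 and 50 are adherence levels, not proportions of subjects above a threshold, so those figures show only that the 17 did not come from a chi-square. The enrolled 91 per arm is ample for the t-test, and even an uncorrected subject-level chi-square of 70% v 50% would have about 79% power.

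These points limit the consequences. They leave the mismatch standing. Nor is this detail left to a statistical analysis plan, because the protocol itself names the test.

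**Conclusion.** The point holds as a mismatch between outcome, test and sample size. The primary outcome is a continuous percentage, the named test needs independent counts, and the 17 per group is a t-test figure under inferred two-sided 5% and 80% power. Those two values rest on inference, though they also reproduce the protocol's 45 and 91.

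Any loss of type I error control is conditional on pooling doses. At mean adherence 60% and 91 per arm it ranges from almost no inflation (6 doses, observed SD 20), through about 14% to 33% (18 doses, true between-subject SD 10 to 20), to about 47% to 71% (144 doses, same SDs). The defect is in the named analysis; the enrolled number does not need to change.

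**What to change.** In Protocol section B, replace the chi-square test for the primary outcome with one of the following:

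- one percentage per subject, calculated as doses taken divided by doses prescribed over that subject's completed questionnaires, compared between arms by a two-sample t-test; or
- a linear mixed model over the two-weekly percentages with a subject random effect.

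The denominator should cover completed questionnaires. If it covered all scheduled ones, a missed questionnaire could count as missed doses.

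Beside the 17 per group, state that it is a t-test figure and give its alpha and power; two-sided 5% and 80% are the values that reproduce it, for the sponsor to confirm.

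The cost is a sentence or two of protocol wording. No extra data, visits or subjects are needed.
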